4.4 Subject Compensation

Each subject will be compensated for any inconvenience that study participation may represent. Specifically, each subject will make 6 total visits to the PI's office (approximately 6 hrs. total time). In return for this time commitment, the subject will receive \$100 per point of enrollment/1st treatment visit, \$50 per follow-up visit at 7-days, \$50 per follow-up visit at 30-days, \$50 per follow-up visit at 60 days, \$50 per follow-up visit at 90 days and \$50 per follow-up visit at 120 days. The total amount of compensation will be \$350 to those subjects who complete all 6 visits.

5.0 SAFETY REPORTING

All adverse events (AEs) that are device or procedure related will be recorded on the AE case report form. Data to be collected will include the description of the AE, onset and resolution dates (or whether the AE is ongoing), severity, management/treatment, outcome, and determination of the relationship to the device and/or procedure. In general, AEs should be reported and classified by the Investigator. The Investigator will determine the relationship of the AE to the device or the study procedure. The Investigator is required to notify the IRB in accordance with local reporting requirements.

All device deficiencies and malfunctions will be recorded on the case report form. If a deficiency or malfunction meets the definition of a product complaint (any written, electronic, or oral communication that alleges deficiencies related to the identity, quality, durability, reliability, safety, effectiveness, or performance of a device after it is released for distribution), a Pulse Biosciences complaint form will be completed by a Clinical or Quality representative.

The Sponsor will ensure safety reporting for the study is conducted in compliance with all pertinent requirements and regulations for all sites participating in this study.

Table 3 summarizes reportable adverse events.

Table 3: Reportable Adverse Events

Description of Event
Infection which requires medical intervention
Bleeding which requires medical intervention
Pain which requires prescription medication for relief

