3.0 PROTOCOL

3.1 Study Purpose and Objectives

The purpose of this study is to evaluate the safety and effectiveness of the CellFX System in patients with cutaneous non-genital warts on all areas of the body, excluding the face.

The study objectives are listed below:

- Evaluate the condition of skin in the treatment areas (erythema, etc.) over the course of 7 to 120 days post-initial NPS treatment
- Evaluate the overall response to NPS treatment by:
 1. Wart clearance (generally accepted as complete clearance of warts from the treated area)
 2. Wart reduction (reduction in the total number of warts)
- Evaluate and assess adverse effects of treatment

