7.5 Protocol Deviations

A protocol deviation is defined as an event where the Investigator or site personnel did not conduct the study according to the study protocol or the Investigator Agreement.

Major deviations include those that involve the primary endpoint, the informed consent process and the inclusion/exclusion criteria of the study, or any deviation that involves or leads to a serious adverse event in a study subject.

Deviations shall be reported to the study Sponsor regardless of whether medically justifiable, pre-approved, or taken to protect the patient in an emergency. Patient specific deviations will be reported on the Case Report Form. Investigators will also adhere to procedures for reporting study deviations to their IRB in accordance with their specific IRB reporting policies and procedures. Deviations from the study protocol will be reviewed and evaluated by the Sponsor on an ongoing basis and, as necessary, appropriate corrective actions put into place.

GCP regulations require that Investigators maintain accurate, complete and current records, including documents showing the dates and reasons for each deviation from the protocol.

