7.8 Case Report Forms and Data Collection

All required data for this study will be collected via case report forms or a web-based electronic data capture (EDC) system and entered in electronic Case Report Forms (eCRFs). Case report forms will be used to record dermatologic medical history, demographic, procedural, and follow-up data, as well as adverse clinical events, protocol deviations and premature study withdrawal which may occur

during the study period. The AEs and incidence of morbidity and mortality will be reviewed with Investigators to assess the safety of the device and the procedure.

Qualified study staff at each clinical site will perform primary data collection drawn from source-document (hospital or clinic chart) reviews. The clinical monitor will perform clinical monitoring, including review of CRFs with verification of study eligibility, informed consent process, procedural data, scheduled follow-up visits and AEs to the source documentation.

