8.3 CRF Completion and Submission

Investigators should complete CRFs in a timely fashion, preferably within 5 business days after subject enrollment or follow-up visit. This will enable timely monitoring visits.

Serious adverse events related to the study device or procedure and device malfunctions should be reported to the study Sponsor within 24 hours of first knowledge of the event. Contact information is included on the CRF form.

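### Section 5.0 requires the AE form only for events judged device- or procedure-related while 7.8 sets no such limit, so events judged unrelated have no assured AE-form or study-database record

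*Protocol*

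**What the plan says.** **Protocol 5.0 (Safety Reporting)** starts with a condition for entry to the form: "All adverse events (AEs) that are device or procedure related will be recorded on the AE case report form". The items then listed for collection include "determination of the relationship to the device and/or procedure", and the decision is assigned: "The Investigator will determine the relationship of the AE to the device or the study procedure". Between these, the paragraph also says in general terms that AEs should be reported and classified by the investigator, with no mention of relatedness. Table 3 lists reportable events (infection or bleeding needing medical intervention, pain needing prescription medication), again without stating relatedness.

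**Protocol 7.8 (Case Report Forms and Data Collection)** has the case report forms hold history, demographic, procedural and follow-up data, "as well as adverse clinical events, protocol deviations and premature study withdrawal which may occur" during the study. It adds: "The AEs and incidence of morbidity and mortality will be reviewed with Investigators to assess the safety of the device and the procedure". Neither statement is confined to related events.

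**Protocol 8.3 (CRF Completion and Submission)** sets a 24-hour report to the sponsor: "Serious adverse events related to the study device or procedure and device malfunctions should be reported".

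**Protocol 8.4 (Source Documents/Record Retention)** requires site case histories to hold relevant observations and data on each subject's condition during the study.

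**Protocol 3.1 (Study Purpose and Objectives)** names safety as part of the purpose and gives as one objective: "Evaluate and assess adverse effects of treatment".

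**The concern.** Relatedness is normally a variable recorded about an adverse event. In the first sentence of 5.0 it decides whether the event must be recorded on the AE form at all. The person making that decision is the unblinded investigator who delivers the treatment, and the protocol states no other adjudication.

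The objective in 3.1 asks which adverse events are effects of treatment. If that question is settled before the form is filled in, the form documents the positive answers and need not document the negative ones. A later reader of the AE data could not ask whether events set aside as unrelated form a pattern. An analysis plan cannot repair this, because it can only work with events that were entered.

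The loss would fall mainly on non-lesional or systemic events. Effects at the study lesions have other traces, since lesions are photographed and rated at each of the five follow-up visits (4.3.2 to 4.3.6). For non-lesional events the protocol's own background gives some reason to keep relatedness open: it describes an immune effect away from the treated tumor in mice and raises a possible immune response to explain clearance of two control warts (both in 1.4). Neither observation shows systemic harm.

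**Working it through.** No arithmetic applies, because the protocol states no rate, count or sample-size figure that turns on this point. The check is a comparison of texts.

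**Step 1. What each text requires for an event judged unrelated**

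| Section | Subject of the text | Relatedness limit? | Effect on an event judged unrelated |
|---|---|---|---|
| 5.0, first sentence | Entry to the AE form | Yes | Not required on the form |
| 5.0, same paragraph | Reporting and classification by the investigator | No | Should be reported; where it is recorded is not stated |
| 5.0, Table 3 | Reportable events | Not stated | Unclear |
| 7.8 | Content of case report forms | No | Recorded |
| 7.8 | Review of AEs, morbidity and mortality | No | Within the review |
| 8.3 | 24-hour report to the sponsor | Yes | No 24-hour report; recording not addressed |
| 8.4 | Site source records | No | In the case history at the site |

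**Step 2. Trace one event.** Take a systemic event that the investigator considers unrelated. A site following the first sentence of 5.0 may leave it off the AE form. A site following 7.8 would enter it. Both act within the protocol. With up to six sites (3.3), the same event could be recorded at one site and not at another.

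**Step 3. Try to reconcile.** If 5.0 is taken as the specific rule and 7.8 as a general list, the contradiction softens, but the filter in 5.0 then governs and the review in 7.8 works from related events only. If 7.8 governs, the first sentence of 5.0 is wrong as written. On either reading 5.0 needs a change. No other section says which prevails.

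**Step 4. Check the internal logic of 5.0.** Relationship is both the condition for entry and an item collected after entry. The form itself is not in the document, so what the item would distinguish (device from procedure, degrees of certainty, or something else) cannot be told. What can be told is that the text does not require the form to show a judgement of unrelated.

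**Step 5. Size.** The protocol gives no number or rate of events judged unrelated. The size is unknown, and no percentage is offered.

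**The case against.** The strongest reply is that 5.0 is the dedicated safety section, 7.8 is a generic list of data types, and collecting related events serves an objective worded as adverse effects of treatment. It can be added that 5.0 is not a uniform filter, given its unrestricted sentence and Table 3; that AEs are assessed at all six visits (4.3); and that monitors verify AEs on the case report forms against source (7.8), with source records kept under 8.4.

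Much of this stands. The site record remains, so it would be wrong to say that events judged unrelated leave no trace. The unrestricted sentence and Table 3 may well lead some sites to report more than the first sentence requires. But they add to the ambiguity and do not resolve it, and neither source records nor verification against source obliges a site to add an unrelated event to the database. An objective about effects of treatment also calls for a reviewable causality judgement.

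A reader might infer more than the text supports:

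- *That 8.3 contradicts 7.8.* It does not. Section 8.3 sets which SAEs go to the sponsor within 24 hours; it does not say which are recorded, and 7.8 sets no expedited-reporting scope.
- *That 4.3 conflicts with 5.0.* Assessing AEs at a visit must come before any relatedness judgement, and 4.3 does not say what is then recorded.
- *That 7.5 conflicts with 5.0.* Section 7.5 counts as major "any deviation that involves or leads to a serious adverse event in a study subject". That classifies deviations and sets no AE-recording rule; subject-level deviations already go on the case report form.
- *That the safety results will be biased.* Under-ascertainment is a risk here, but nothing in the document demonstrates it, and the protocol plans no all-cause or treated-versus-control AE rate that would be distorted.

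**Conclusion.** The point holds as an unreconciled recording rule between 5.0 and 7.8, with a relatedness filter in 5.0 placed ahead of the form meant to document relatedness. Events judged unrelated have no guaranteed AE-form or study-database record, recording may differ by site, and the causality judgement cannot be re-examined from the AE form. The morbidity and mortality review in 7.8 may therefore rest on incomplete data. The effect cannot be sized and no bias is shown, so this is an inexpensive improvement worth making in a pivotal study with safety in its stated purpose, not a defect that invalidates its safety conclusions.

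The conclusion assumes that sites work from the protocol text. The case report forms, the monitoring plan and any SAP are not shown. If the AE form already takes all events, the practical effect would be small, but the first sentence of 5.0 would still need to match it.

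**What to change.** 1. In 5.0, require all adverse events to be recorded on the AE form regardless of relationship, and make relationship a field with an explicit unrelated category beside device and procedure.
2. Align 5.0 with 7.8 so that one rule states which events enter the case report forms and feed the morbidity and mortality review. State in the same place how Table 3 relates to that rule.
3. As a secondary improvement, and not to cure a contradiction, extend the 24-hour report to the sponsor in 8.3 to all SAEs regardless of relationship.

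The cost is protocol and form wording, modest extra data entry in about 60 subjects (3.3), and a possibly higher reported AE count, which the relationship field allows to be read correctly. The change touches data capture and reporting only. It is best made before enrollment, because events never entered may be hard to reconstruct later.

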5.1 Follow-Up and Reporting

All patients enrolled, and devices used in the clinical investigation will be accounted for in the final report. All reasons for exclusion from analysis will be carefully documented. Similarly, for all subjects and devices included in an analysis population, the measurements of all-important variables must be accounted for at all relevant time points. Additional information that is available on patients screened for entry but not enrolled will also be summarized.

6.0 STUDY MANAGEMENT

6.1 Sponsor Ethical and Regulatory Considerations

As the Sponsor of this clinical study, Pulse Biosciences has the overall responsibility for the conduct of the study, including assurance that the study meets US federal and local regulatory requirements appropriate to the conduct of the study and is conducted according to Good Clinical Practices (GCP), 21 CFR 812, 820, 50, 54, and 56, Declaration of Helsinki, applicable IRB requirements, as well as Sponsor general duties as described in ISO 14155:2011/AC: 2011. In this study, Pulse Biosciences will have certain direct responsibilities and may delegate other responsibilities to qualified consultants and/or a Contract Research Organization (CRO).

The protocol and any amendments will be submitted to each site's IRB for formal approval of the study. All subjects considered for this study will be provided a consent form describing this study and providing sufficient information for them to make an informed decision about their participation.

6.2 Subject Confidentiality

Subject confidentiality will be maintained throughout the clinical study. To maintain confidentiality, all evaluation forms, reports and other records will be identified by a unique subject identification code (ID number). All study records will be kept in a locked file cabinet and clinical information will not be released without written permission of the subject, except as necessary for monitoring by the FDA. The Investigator must also comply with all applicable privacy regulations (e.g., Health Insurance Portability and Accountability Act of 1996).

7.0 SPONSOR RESPONSIBILITIES

7.1 Selection of Clinical Sites

The primary requirements of site and Investigator selection and continued participation in the Trial are: adequate experience, commitment to safety, consistency in adherence to the protocol, and patient volume. Participating sites will be screened to ensure they have adequate numbers of eligible patients who are representative of the target population. The clinical site must have facilities that are capable of processing patients in the manner prescribed by the protocol.

The study Sponsor, Pulse Biosciences, and its designees will select qualified Investigators, ship or deliver devices only to participating Investigators, obtain signed study agreements, and provide Investigators with the information necessary to conduct the study.

7.2 Site Training

The training of appropriate clinical site personnel will be the responsibility of the Sponsor or designee. The Investigator is responsible for ensuring that his/her staff conduct the study according to the protocol. To ensure proper device usage, uniform data collection, and protocol compliance, the Sponsor or designee will present a formal training session to study site personnel which will review the instructions for use of the device, the study protocol, methods for soliciting data from alternative sources, schedules for follow-up with the study site coordinators, and regulatory requirements. Detailed feedback regarding completion of forms will be provided by the Sponsor or designee through the regular site monitoring.

7.3 Investigator Training

The Sponsor will provide appropriate Investigator training on the use of the NPS System. Training will take place prior to the initiation of the clinical investigation. Training will address topics including indications for use of the device, management of complications, and instructions to subjects. Training will be documented for each physician on a training log, signed by both the physician and training representative

7.4 Monitoring of Study Sites

7.4.1 Monitoring Methods

Monitoring functions will be conducted by the Sponsor. Specific monitoring requirements are detailed in the study specific Monitoring Plan maintained in the Pulse Biosciences clinical study project files.

All monitoring activities shall be documented in a written report. Corrective action will be taken to resolve any issues of noncompliance. If Pulse Biosciences finds that an Investigator is not complying with the executed Investigator Agreement, the study protocol, the applicable laws and regulations, or the requirements of the reviewing IRB, prompt action will be taken to secure compliance. Pulse Biosciences will reserve the right to suspend or terminate the participation of the Investigator or the study site.

7.4.2 Monitoring Visits

Scheduled monitoring visits to the clinical study site may occur at the following times: prior to the start of the study, interim visits throughout the clinical study as required per the monitoring plan, and upon completion of the clinical study. Sites that enroll rapidly may be visited more frequently

at Pulse Biosciences discretion. A final Close-Out Visit will be conducted upon completion of the entire clinical study or at the time, a site is terminated.

7.5 Protocol Deviations

A protocol deviation is defined as an event where the Investigator or site personnel did not conduct the study according to the study protocol or the Investigator Agreement.

Major deviations include those that involve the primary endpoint, the informed consent process and the inclusion/exclusion criteria of the study, or any deviation that involves or leads to a serious adverse event in a study subject.

Deviations shall be reported to the study Sponsor regardless of whether medically justifiable, pre-approved, or taken to protect the patient in an emergency. Patient specific deviations will be reported on the Case Report Form. Investigators will also adhere to procedures for reporting study deviations to their IRB in accordance with their specific IRB reporting policies and procedures. Deviations from the study protocol will be reviewed and evaluated by the Sponsor on an ongoing basis and, as necessary, appropriate corrective actions put into place.

GCP regulations require that Investigators maintain accurate, complete and current records, including documents showing the dates and reasons for each deviation from the protocol.

7.6 Device Accountability

The Investigator shall maintain adequate records of the receipt and disposition of all study devices according to 21 CFR 812.140 (a)(2). At the completion of the study, all devices shall be returned to the Sponsor. The Investigator's copy of the Device Accountability Log must document devices that have been returned to the Sponsor.

The device accountability log will include records of receipt, use or disposition of a device that relate to:

1. The type and quantity of the device, the dates of its receipt, and the serial or lot number.
2. The names of all persons who received, used, or disposed of each device.
3. Why and how many units of the device have been returned to the Sponsor, or otherwise disposed of.

7.7 Data Management

Pulse Biosciences and Data Management designees will oversee and/or perform all data management functions. Data management functions include database development, system maintenance, user training, data queries, and report generation. The Principal Investigator and /or study staff are responsible for accuracy and completeness of all study data recorded.

7.8 Case Report Forms and Data Collection

All required data for this study will be collected via case report forms or a web-based electronic data capture (EDC) system and entered in electronic Case Report Forms (eCRFs). Case report forms will be used to record dermatologic medical history, demographic, procedural, and follow-up data, as well as adverse clinical events, protocol deviations and premature study withdrawal which may occur

during the study period. The AEs and incidence of morbidity and mortality will be reviewed with Investigators to assess the safety of the device and the procedure.

Qualified study staff at each clinical site will perform primary data collection drawn from source-document (hospital or clinic chart) reviews. The clinical monitor will perform clinical monitoring, including review of CRFs with verification of study eligibility, informed consent process, procedural data, scheduled follow-up visits and AEs to the source documentation.

7.9 Sponsor Data Retention

Pulse Biosciences will maintain copies of correspondence, data, shipment of devices, adverse device effects, Investigator agreements and other records related to the clinical trial. All study records and reports will remain on file at the sites for a minimum of 2 years after completion of the Study and will further be retained in accordance with local guidelines as identified in the clinical study agreement. Study records are to be discarded only upon notification by the study Sponsor. The Investigator must contact the study Sponsor before the destruction of any records and reports pertaining to the study to ensure they no longer need to be retained. In addition, the Sponsor should be contacted if the Investigator plans to leave the investigational site. All required data for this study will be collected on standardized CRFs or an electronic data capture system. All information and data sent to the Sponsor concerning subjects or their participation in this study will be considered confidential. All data used in the analysis and reporting of this evaluation will be used in a manner without identifiable reference to the subject. The principal Investigator consents to visits by the Sponsor and its authorized representatives and the U.S. Food and Drug Administration or any other local governmental body to review the study subjects' medical records including any test or laboratory data that might have been recorded on diagnostic tests media (e.g., photographs, etc.).

